#### Definition of high daily dose of various inhaled corticosteroids in relation to patient age

Inhaled corticosteroid	Threshold daily dose in $\mu\text{g}$ considered as high	
	Age 6–12 years	Age >12 years
Beclomethasone dipropionate	$\geq 800$ (DPI or CFC MDI) $\geq 320$ (HFA MDI)	$\geq 2000$ (DPI or CFC MDI) $\geq 1000$ (HFA MDI)
Budesonide	$\geq 800$ (MDI or DPI)	$\geq 1600$ (MDI or DPI)
Ciclesonide	$\geq 160$ (HFA MDI)	$\geq 320$ (HFA MDI)
Fluticasone propionate	$\geq 500$ (HFA MDI or DPI)	$\geq 1000$ (HFA MDI or DPI)
Mometasone furoate	$\geq 500$ (DPI)	$\geq 800$ (DPI)
Triamcinolone acetonide	$\geq 1200$	$\geq 2000$

Notes: 1) Designation of high doses is provided from manufacturers' recommendations where possible. 2) As chlorofluorocarbon (CFC) preparations are being taken from the market, medication inserts for hydrofluoroalkane (HFA) preparations should be carefully reviewed by the clinician for the equivalent correct dosage. DPI: dry powder inhaler; MDI: metered-dose inhaler.

A further analysis will also be taken to generate Receiver Operating Characteristic (ROC) curves to determine if a cut-off of high specificity and sensitivity can be determined for the (C-)ACT and ACQ in predicting which children are likely to experience a significant exacerbation in asthma following LAIV. The ACQ is only validated for children age 6 and over: thus, this analysis will be performed using both the complete dataset and also after excluding children under age 6 years.

Data analysis will be undertaken by PHE Immunisation Department Statistician and members of the Clinical Trial Team where appropriate.

The results of the study will be submitted for peer-reviewed journal publication(s). If requested, anonymised data will be provided to the vaccine manufacturers, and comparative analysis of results may be performed.

No interim analyses are planned.

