## 1.3 STUDY RATIONALE & JUSTIFICATION

The JCVI has recommended annual influenza vaccination for all children 2-16 years of age. The programme commenced using Fluenz in the 2013/2014 influenza season, was initially restricted to children under 4 years of age for logistic reasons, but is subsequently being expanded over the next few years to include all children under 16 years.

To date, there are only limited data available regarding the safety of LAIV in children with “severe” asthma requiring high dose inhaled corticosteroid therapy (or more intensive treatment). In the SNIFFLE-1 and -2 studies, only 49 children were included requiring BTS Step 4+ treatment. This lack of data is reflected in the current guidance from Department of Health:

“There is limited safety data on children who are currently taking a high dose of an inhaled steroid – Budesonide >800 mcg/day or equivalent (e.g. Fluticasone >500 mcgs/day) – such children should only be given LAIV on the advice of their specialist.”

This study will enrol 840 children with a history of asthma or recurrent wheezing (target 420 at BTS 4+ or greater, the remaining 420 participants at lesser levels of treatment), to obtain further safety data relating to the administration of LAIV in this group of children and thus inform UK guidance with regard to LAIV.

The study includes an assessment of influenza virus shedding following LAIV. Though efficacy of the vaccine has been maintained in the first few years of LAIV use in the UK, this is not so in the USA where it has been used for the last decade. The unique cohort included in this study provide an opportunity to assess viral shedding in the period immediately after vaccination, through parental collection of nasal swabs at three time points in the week following vaccination, which will be posted in prepaid bags directly to the testing laboratory at PHE Colindale. This will likely be 24 hours, 72 hours and 6 days after vaccination but these time points will be confirmed nearer the start of the study based on international data which is being gathered and published now. There may be a correlation between vaccine shedding and adverse events following vaccination. The data will also help inform as to whether there is a link between vaccine shedding and previous exposure to influenza vaccines including previous LAIV, an issue which might explain the apparent lower efficacy of LAIV in the USA compared to UK and Finland.

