### 3.1.2. SECONDARY STUDY OUTCOMES

1. Incidence of adverse events (AE) and serious adverse events (SAEs) in children receiving LAIV:
  - AEs occurring up to 72 hours after LAIV.
  - SAEs unrelated to asthma symptoms with onset up to 72 hours after LAIV
  - Incidence of a 'significant exacerbation' in asthma, defined as:
    - i. At least 3 day course of oral steroids following an unscheduled contact with a healthcare professional; OR
    - ii. Unscheduled visit to an Emergency department or admission to hospital for treatment of asthma symptoms, requiring systemic corticosteroids
2. Incidence and extent of viral shedding in children and young people receiving LAIV during the 2016/17 influenza season, using quantitative analysis of consecutive nasal swabs obtained up to 10 days following LAIV. These data will be correlated with the incidence of adverse events related to asthma over the same time period.

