#### 8.1.3 ASTHMA CONTROL ASSESSMENT PRE AND 4 WEEKS POST VACCINATION

Participants' families will be asked to complete a questionnaire to determine their child's asthma symptoms and control, using a validated tool at visit 1:

- In children age 2-4 years: TRACK questionnaire (Appendix 1)
- In children age 5-11 years: C-ACT questionnaire (Appendix 2a)
- In children age 12+ years: ACT questionnaire (Appendix 2b)

As part of the CRF, the questions on the Asthma Control Questionnaire (ACQ, Appendix 3) will also be completed. While the (C-)ACT and TRACK questionnaires assess asthma symptoms over the preceding 4 weeks, the ACQ assesses symptoms and control over the preceding 7 days and also includes lung function; the ACQ may therefore be more representative of asthma control at the time of vaccination. The (C-)ACT will be completed first, before the ACQ.

Families will be asked to complete a further questionnaire 4 weeks after vaccination. In general, this will be done using an online questionnaire. Families will be asked at their first

visit as to whether they prefer to be contacted by telephone by the study team, or receive an email request with a link to a secure, online survey. Either way, the survey will take 2-3 minutes to complete. A guide for the telephone call is provided in Appendix 6. These data will be recorded on a CRF.

If the family fails to respond to the email request, the local study team will attempt to contact the family by telephone. If, after three attempts (on three separate days), the local study team is unable to contact the family, the child will be deemed lost to follow up and this will be documented on the CRF, which will then be closed.

At the Royal Brompton, participants will be invited to return to hospital for the 4 week follow-up (which will, in general, coincide with a routine clinic follow-up appointment). The follow-up questionnaires will be completed at this visit, along with some further repeat assessments (section 8.3).

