### 9.2 SAMPLE SIZE ESTIMATION

Sample size is based on the primary objective of comparing the proportion of participants who experience a significant change in asthma control, as measured by a change in at least 3 points *and* from  $\geq 20$  on the (C-)ACT (good control) to  $< 20$  (sub-optimal control) in each group (BTS  $\leq 3$  vs BTS 4/5), or vice versa. In the SNIFFLE-2 study, such a change (one way or the other) was seen in about 20% of children (10% worse, 10% better).

A sample of 400 children in each group will provide sufficient power (5% significance level, 80% power) to detect an improvement in 10% vs deterioration in 17.5%, allowing for 10% attrition. In SNIFFLE-2, follow-up at four weeks was 89%. If the proportion of participants with a change in ACT score is less than this, with only 5% improving and 10% getting worse, a sample size of about 420 would provide a similar level of power. This would represent a conservative assumption in the proportions changing. For comparing the average change pre to post vaccination in ACT score between the severe and non-severe groups, the standard deviation of change from SNIFFLE-2 was used (about 3 units). With a sample size of 400 in each group the detectable difference is 0.6 units between the groups (80% power, 5% significance).

Assuming that about 1% of participants experience a significant deterioration in asthma control (as defined in 3.1.2 above), then the 95% CI for a significant deterioration will be from 0.027% to 2.54%. If 0/400 are observed the upper 95% CI is 0.92%.

---

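### The ROC search for a (C-)ACT or ACQ cut-off rests on about 7 expected exacerbations, with no stated confidence interval or internal validation, and leaves out TRACK at ages 2-4

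*Combined protocol and SAP*

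**What the plan says.** The last analysis in section 9.3, after the inhaled corticosteroid table, draws ROC curves "to determine if a cut-off of high specificity and sensitivity can be determined for the (C-)ACT and ACQ" for predicting which children go on to a significant exacerbation. It is run on the whole dataset and repeated without children under 6, because "The ACQ is only validated for children age 6 and over".

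The outcome is defined in sections 3.1.2 and 9.1. It has two limbs: "At least 3 day course of oral steroids following an unscheduled contact with a healthcare professional", or an unscheduled emergency visit or admission for asthma needing systemic corticosteroids. Respiratory events are collected for one month (section 7.1). The only planning rate is in section 9.2: "Assuming that about 1% of participants experience a significant deterioration in asthma control", with a reference to 3.1.2.

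Section 8.1.3 assigns one control score by age: TRACK at 2-4, C-ACT at 5-11, ACT from 12. The ACQ is completed in addition. TRACK is not named in the ROC paragraph, although section 9.3 gives it a threshold of 80 for the primary outcome, alongside 20 for the ACT.

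For the ROC analysis the plan gives no expected number of events, no rule for choosing the cut-off, no confidence interval for AUC, sensitivity or specificity, and no internal validation.

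**The concern.** A cut-off that is chosen and judged on the same children inherits the chance pattern of the events in that sample. With few events, the chosen value moves widely between samples, and its reported sensitivity and specificity are, on average, better than it would achieve in new children.

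There is also a gap in coverage. Children aged 2-4 have no (C-)ACT score. They enter the complete-dataset analysis only through the ACQ, which the plan itself treats as unvalidated at that age, while their TRACK score is collected and goes unused here.

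The study is meant to inform UK guidance on LAIV (section 1.3). A reported cut-off could be taken at face value, both for its accuracy and as a marker of risk caused by the vaccine. The design cannot supply the second reading, since every child is vaccinated.

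**Working it through.** **1. The plan's own rate.** Section 9.2 attaches a 95% interval to the 1% rate. The exact (Clopper-Pearson) interval for 4/400 is 0.273% to 2.54%. The upper limit matches the plan. The printed lower limit of 0.027% is ten times too small and looks like a decimal slip, which does not matter here. The exact upper limit for 0/400 is 0.92%, as printed. So 1% is the plan's working rate for this outcome.

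**2. Expected events.** Inputs: "This study will enrol 840 children with a history of asthma or recurrent wheezing" (section 1.3); 89% four-week follow-up in SNIFFLE-2, and a sample size "allowing for 10% attrition" (section 9.2).
- 840 × 0.89 × 0.01 = 7.5
- 840 × 0.90 × 0.01 = 7.6
- no loss: 840 × 0.01 = 8.4
- binomial 95% range for 748 children at 1%: 3 to 13 events
- at the plan's upper limit: 748 × 0.0254 = 19

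**3. Events available to the (C-)ACT curve.** The documents give no age split. Assuming 10% to 40% of children are aged 2-4, with the same event rate at all ages:
- 840 × 0.89 × 0.90 × 0.01 = 6.7
- 840 × 0.89 × 0.60 × 0.01 = 4.5

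**4. Precision.** Exact 95% intervals for sensitivity are 42% to 99.6% for 6 of 7 events detected, and 59% to 100% for 7 of 7.

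For the AUC (A), with n₁ events and n₀ non-events, the Hanley-McNeil formula is SE² = [A(1−A) + (n₁−1)(a−A²) + (n₀−1)(b−A²)] / (n₁n₀), where a = A/(2−A) and b = 2A²/(1+A). With A = 0.70, n₁ = 7 and n₀ = 741, a = 0.538 and b = 0.576. Then SE = 0.112, and the 95% interval is 0.70 ± 0.22, or 0.48 to 0.92. With 8 events SE = 0.104, giving 0.50 to 0.90.

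**5. Optimism of a selected cut-off.** Simulation of 748 children with an integer score, taking the cut-off that maximises the Youden index (sensitivity + specificity − 1). The score distributions and the Youden rule are assumptions, since the plan gives neither.

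| Assumed score | Events | True AUC | Apparent Youden | Delivered by chosen cut-off |
|---|---|---|---|---|
| mean 19, SD 4.5, range 5-25 | 8 | 0.70 | 0.40 | 0.25 |
| same | 19 | 0.70 | 0.35 | 0.26 |
| same | 8 | 0.50 | 0.17 | 0.00 |
| mean 20, SD 4, range 0-27 | 7 | 0.70 | 0.41 | 0.25 |
| same | 50 | 0.70 | 0.32 | 0.27 |

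In the 7-event row with true AUC 0.70, apparent sensitivity averages 77% against a true 60%, and the chosen cut-off runs from 14 to 22 points (5th to 95th percentile). With 50 events it runs from 16 to 20.

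The AUC itself is not inflated: its simulated mean is 0.70 when the truth is 0.70, because a raw score with a fixed direction involves no fitting.

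**6. Scales.** The C-ACT in Appendix 2a has four items scored to 3 and three scored to 5: 4 × 3 + 3 × 5 = 27, range 0-27. The ACT in Appendix 2b has five items scored 1 to 5, range 5-25. A raw score of 18, say, is not the same position on the two scales.

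**The case against.** The strongest reply is that this is one exploratory analysis, outside the primary and secondary outcomes, and that it asks whether a good cut-off exists, so no is an allowed answer. That stands. A reader might infer that the search would probably produce a spurious cut-off from a worthless score. The simulations do not support that if the plan's demand for high values on both measures is taken seriously. With true AUC 0.50, some cut-off reached 70% on both sensitivity and specificity in only 0.8% of runs with 8 events and 2.0% with 7, and 80% on both in essentially none. The problem is inflated performance when there is some real signal, not discovery from nothing.

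Four other stronger readings also fail.
- That C-ACT and ACT will share one new cut-off: the plan does not say so. The bracketed name is its shorthand for either instrument, and it refers to curves in the plural. It simply leaves the point open.
- That the plan overlooks the ACQ's age limit: it states the limit and schedules the analysis without under-6s. That repeat still gives ages 2-4 no usable predictor.
- That omitting TRACK causes the instability: it does not. It is a gap in coverage, and it reduces the events behind the (C-)ACT curve.
- That a cut-off would be used to withhold LAIV: no passage says this. The lack of vaccine specificity comes from the uncontrolled design, not from the ROC method, and the plan's own wording for the outcome is temporal.

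The event count could also exceed 1%. Even at 2.54%, about 19 events leave a gap of 0.35 against 0.26.

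**Conclusion.** The point holds in this form. On the plan's own inputs the ROC analysis has about 7.5 expected events (7.5 to 8.4 across the attrition choices, binomial range 3 to 13), and perhaps 4.5 to 6.7 for the (C-)ACT under an assumed 10% to 40% share of ages 2-4. A data-selected cut-off is expected to be imprecise, and its Youden index to be overstated by about 0.15 (0.40 − 0.25) if the true AUC is 0.70. That figure depends on the assumed score distribution and the Youden rule; two different distributions gave nearly the same answer. Optimism is an average property, so a particular result need not be too good, and a finding of no cut-off remains open. The primary analysis is not affected.

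**What to change.** Amend the ROC paragraph in section 9.3 before analysis.

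1. Make the main predictive analysis the baseline thresholds the plan already uses: (C-)ACT below 20, and TRACK below 80 at ages 2-4. Report sensitivity and specificity with exact 95% confidence intervals.
2. Report AUC with a 95% confidence interval. No optimism correction is needed for a raw score.
3. Treat any data-derived cut-off as exploratory. State the selection rule in advance and give bootstrap-corrected sensitivity and specificity, repeating the selection in each resample.
4. Do not pool raw C-ACT and ACT scores to derive one new cut-off.
5. Give the expected number of events, and describe the result as prognostic for exacerbation after vaccination, not as LAIV-specific risk.

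This uses data already collected and costs SAP wording and a bootstrap. The downside is that the paper cannot claim a firm new cut-off. Instrument-specific estimates will also be very imprecise: if about 7 events split evenly over three instruments (an assumption), each has 2 or 3, and detecting 2 of 3 has an exact interval of 9% to 99%.

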## 10 DATA MANAGEMENT

### 10.1 DATA COLLECTION

The following data will be collected:

- Patient demographics
- Current health to establish safety of immunisation
- Vaccination history:
  - previous exposure to influenza vaccine
  - previous reactions to vaccines
- Past medical history:
  - Medical indication for influenza vaccination or routine
  - Asthma status
  - Active Allergic rhinitis
  - Current Medication
  - Other atopy: allergic rhinitis, eczema, other food allergies

Data will be collected by paper CRF and then transferred to Public Health England, with participants identified by study number. Patient identifiable information (e.g. names, email addresses) will be transferred to Public Health England via a GSI gateway secure server. This is necessary to facilitate the swabbing phase of the study. Specific consent to share patient identifiable information with Public Health England will be included on the study consent form.

### 10.2 DATA RECORDS

Paper records will be maintained at local sites for all participants enrolled in the study. CRFs will be completed at each visit, reviewed by the coordinating centre and then sent to PHE Colindale. A database will be constructed at PHE Colindale to record the information collected in the CRFs. As the data are being entered, the CRFs will be monitored for completion errors or omissions. When such a problem is identified the card will be photocopied and the field for correction marked. Any corrections necessary will be made by the study team according to GCP and returned to PHE Colindale, where the database will be updated accordingly and the photocopy filed with the original CRF.

Information from CRFs will be entered at PHE Colindale into an Access database. Data will be entered twice by different members of staff into identical Access study databases which will be compared using an Access programme which compares the data in the two databases and identifies data entry errors. These will then be corrected.

Study data will be kept for 10 years following the child's 18th birthday, and then disposed of securely. Local paperwork will be kept as part of the patient notes/CRF as per local policy.

## 11 ADMINISTRATIVE AND REGULATORY ISSUES

### 11.1 CLINICAL TRIALS AUTHORISATION

This study has Clinical Trials Authorisation from the UK Competent Authority; MHRA, Eudra CT registration no. 2016-002352-24. The study is also registered at Clinicaltrials.gov, reference: NCT02866942.

### 11.2 ETHICS APPROVAL

The Chief Investigator has obtained the required approvals from the West Midlands-Edgbaston Research Ethics Committee. The study will be submitted for Site Specific Assessment (SSA) at each participating NHS Trust. The Chief Investigator will require a copy of the Trust R&D approval letters before accepting participants into the study. The study will be conducted in accordance with the recommendations for physicians involved in research on human subjects adopted by the 18th World Medical Assembly, Helsinki 1964 and later revisions.

### 11.3 INFORMED CONSENT AND PARTICIPANT ASSENT

Consent to enter the study must be sought for each participant only after a full explanation has been given, an information leaflet offered and time allowed for consideration. Signed consent from the parent/legal guardian should be obtained. In children over 8 years of age, participant assent will also be sought. The right of the parent/guardian to refuse to participate without giving reasons must be respected. After the participant has entered the trial the clinician remains free to give alternative treatment to that specified in the protocol at any stage if he/she feels it is in the participant's best interest, but the reasons for doing so should be recorded. In these cases the participants remain within the study for the purposes of follow-up and data analysis. All participants are free to withdraw at any time from the protocol treatment without giving reasons and without prejudicing further treatment.

### 11.4 CONFIDENTIALITY

Participants' identification data will be required for the registration process. Both Imperial College Healthcare NHS Trust / Imperial College London and Public Health England are registered under the Data Protection Act. The Chief Investigator will preserve the confidentiality of participants taking part in the study under the Data Protection Act.

### 11.5 INDEMNITY

Imperial College Healthcare NHS Trust holds standard NHS Hospital Indemnity and insurance cover with NHS Litigation Authority for NHS Trusts in England, which apply to this study.

### 11.6 SPONSOR

Imperial College Healthcare NHS Trust will act as the main Sponsor for this study. Delegated responsibilities will be assigned to the NHS trusts taking part in this study.

## 11.7 FUNDING

Funding has been secured from the Department of Health Policy Research Programme (NVEC039/0031) awarded to [name], Public Health England.

## 11.8 AUDITS

The study may be subject to inspection and audit by Imperial College Healthcare NHS Trust under their remit as sponsor and other regulatory bodies to ensure adherence to GCP and the NHS Research Governance Framework for Health and Social Care (2nd edition).

## 11.9 MONITORING

The JRCO Clinical Trial Monitor will be responsible for monitoring this study throughout its duration, including site initiation visit and close out visit. The monitor will conduct a risk assessment and compile a monitoring plan accordingly. After each monitoring visit the monitoring report will be sent to the chief investigator and any action point that needs to be completed will be done so by the study team.

## 12 STUDY MANAGEMENT

The day-to-day management of the study will be co-ordinated through [name] (CI).

## 13 PUBLICATION POLICY

All publications and presentations relating to the study will be authorised by the Trial Steering Committee and the Department of Health. If there are named authors, these will include at least the trial's Chief Investigator, Statistician and Trial Coordinator. Where the journal's policy allows, all site PIs will be listed as collaborators for any publications generated from the study.

Members of the Data Monitoring Committee will be listed and contributors will be cited by name if published in a journal where this does not conflict with the journal's policy.

